#### 10.1.2. Handling of missing data

##### 10.1.2.1. Dates

When partially completed dates (i.e. with missing day or month) are used in calculations, the following standard rules will be applied:

- A missing day will be replaced by 15
- A missing day and month will be replaced by June 30th.

The following exceptions apply:

- Adverse event start dates with missing day:
  - If the event starts in the same month as at least one of the study doses, the contents of AE.AESTRTPT (the flag indicating if the event occurred before or after vaccination) will be used to complete the date. If 'after vaccination' is selected, the imputed start date will match the first (or only) study dose given during that month. If 'before vaccination' is selected, the imputed date will be one day before the first (or only) study dose given during that month.

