12.5.8. Detecting and recording adverse events, serious adverse events and pregnancies

A pDiary, hereafter referred to as Subject Diary will be used in this study to capture solicited and unsolicited adverse events. The subject should be trained on how and when to complete each field of the Subject Diary.

The subjects will be instructed to contact the investigator immediately should the subjects manifest any signs or symptoms they perceive as serious.

Subject Diary training should be directed at the individual(s) who will perform the measurements of adverse events and who will enter the information into the Subject Diary. This individual may not be the subject, but if a person other than the subject enters information into the Subject Diary, this person's identity must be documented in the Subject Diary. Any individual that makes entries into the Subject Diary must receive training on completion of the Subject Diary at the time of the visit when Subject Diary is dispensed. This training must be documented in the subject's source record.

CONFIDENTIAL209538 (NTHI MCAT-009)
Protocol Amendment 1 Final

At each NTHi-Mcat vaccination visit, diary cards will be provided to the subject. The subject will be instructed to measure and record the axillary body temperature, and any solicited local/general AEs (i.e. on the day of vaccination and during the next 6 days) or any unsolicited AEs (i.e. on the day of vaccination and during the next 29 days occurring after vaccination. The subject will be instructed to return the completed diary card to the investigator at the next study visit.

- Collect and verify completed diary cards during discussion with the subject on Day 121; Day 181; Day 271 (Visit 4_1, Visit 4_3, Visit 4_6), and Day 181; Day 241; Day 331 (Visit 6_1, Visit 6_3, Visit 6_6) in the Sh_NTHi-Mcat groups and on Day 31 (Visit 2) and Day 91 (Visit 4) in the NTHi-Mcat group.
- Any unreturned diary cards will be sought from the subject through telephone call(s) or any other convenient procedure.

The investigator will transcribe the collected information into the eCRF in English.

12.5.8.1. Time period for detecting and recording adverse events, serious adverse events and pregnancies

All AEs during 30 days following administration of each dose of NTHi-Mcat study vaccine (Day 1 to Day 30) must be recorded onto/into the appropriate section of the eCRF, irrespective of intensity or whether or not they are considered vaccination-related.

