**Table 1 Study groups, treatment and epochs foreseen in the study**

Study Groups	Number of subjects	Age (Min-Max)	Treatment name	Epochs (Blinding)	
				Epoch 001 (open-label)	Epoch 002 (open-label)
Sh_NTHi-Mcat_1	135	50 – 80 years	Shingrix / NTHi-Mcat	●	●
Sh_NTHi-Mcat_3	135	50 – 80 years	Shingrix / NTHi-Mcat	●	●
Sh_NTHi-Mcat_6	135	50 – 80 years	Shingrix / NTHi-Mcat	●	●
NTHi-Mcat	135	50 – 80 years	NTHi-Mcat	●	●

- **Treatment allocation:** Subjects will be allocated to a study group using an automated, electronic System Built for Internet Randomization (SBIR). The randomization algorithm will use a minimization procedure accounting for age category (50–59, 60–69, 70–80 years of age), smoking status (current or former smoker), and centre. Minimization factors will have equal weight in the minimization algorithm.
- **Blinding:** open-label.
- **Data collection:** Electronic Case Report Form (eCRF). Telephone contact. Solicited and unsolicited symptoms will be collected using a subject Diary (paper diary [pDiary]).
- **Safety monitoring:** Subjects will be observed for at least 60 minutes after each NTHi-Mcat vaccination for any immediate reactions. Solicited local and general AEs occurring during a 7-day follow-up period after each NTHi-Mcat vaccination (i.e. the day of vaccination and the 6 subsequent days) and unsolicited AEs occurring during a 30-day follow-up period after each NTHi-Mcat vaccination (i.e. the day of vaccination and the 29 subsequent days), will be reported via diary cards. In addition, subjects will be asked at Phone contacts if there were any safety concerns in the 7-day follow-up period after each NTHi-Mcat vaccination; this information will be recorded via the appropriate section of the eCRF. Finally, safety assessments will be performed during each clinic visit and safety follow-up calls to collect information on AEs leading to withdrawal, serious adverse events (SAEs), SAEs related to study participation or to a concurrent GSK medication/vaccine, pregnancies, potential immune-mediated diseases (pIMDs), throughout the whole study period.

**CONFIDENTIAL**209538 (NTHI MCAT-009)  
Statistical Analysis Plan Amendment 2**3. OBJECTIVES AND ENDPOINTS**

Objectives	Endpoints
Primary	

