Secondary	
Within group assessment
 
The percentage of subjects with at least 1 local adverse event (AE) (solicited and unsolicited), with at least 1 general AE (solicited and unsolicited) and with any AE during the 7-days solicited follow-up period and the 30-days follow-up period will be tabulated by group with exact 95% CI after each NTHi-Mcat vaccine dose and overall. The percentage of NTHi-Mcat doses followed by at least 1 local AE (solicited and unsolicited), by at least 1 general AE (solicited and unsolicited) and by any AE will be tabulated by group with exact 95% CI. The same calculations will be performed for AEs rated as Grade 3, for AEs causally related to vaccination and Grade 3 AEs causally related to vaccination.
 
The percentage of subjects reporting each individual solicited local and general AE during the 7-days solicited follow-up period after each dose of NTHi-Mcat vaccine will be tabulated by group with exact 95% CI. The percentage of NTHi-Mcat doses followed by each individual solicited local and general AE will be tabulated by group with exact 95% CI.
 
Fever will be reported per 0.5°C cumulative increments.
 
For all solicited symptoms, the same tabulation will be performed for Grade 3 AEs.
 
The verbatim reports of unsolicited symptoms will be reviewed by a physician and the signs and symptoms will be coded according to the Medical Dictionary for Regulatory Activities (MedDRA) Dictionary for Adverse Event Terminology. The percentage of subjects with at least 1 report of unsolicited adverse event classified by the MedDRA and reported up to 30 days after NTHi-Mcat vaccinations will be tabulated by group with exact 95% CI. The same tabulation will be performed for Grade 3 unsolicited adverse events, for unsolicited adverse events with a causal relationship to vaccination and for Grade 3 AEs causally related to vaccination.
 
The number of subjects who experienced any serious adverse event (SAE) or any potential immune-mediated disease (pIMD) from Day 1 to Day 331 and from Day 331 to Day 661 will be reported.
 
The number of subjects who experienced any AE leading to study withdrawal, from first vaccination up to study conclusion, or any SAE related to study participation or concurrent GSK medication/vaccination, during the entire study period, will be reported.
 
A summary of subjects reporting concomitant medication/product will be provided.

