#### 10.1.2. Handling of missing data

##### 10.1.2.1. Dates

When partially completed dates (i.e. with missing day or month) are used in calculations, the following standard rules will be applied:

- A missing day will be replaced by 15
- A missing day and month will be replaced by June 30th.

The following exceptions apply:

- Adverse event start dates with missing day:
  - If the event starts in the same month as at least one of the study doses, the contents of AE.AESTRTPT (the flag indicating if the event occurred before or after vaccination) will be used to complete the date. If 'after vaccination' is selected, the imputed start date will match the first (or only) study dose given during that month. If 'before vaccination' is selected, the imputed date will be one day before the first (or only) study dose given during that month.

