**10.1.3.5. Onset day**

The onset day for an event (e.g. AE, medication, vaccination) is the number of days between the last study vaccination and the start date of the event. This is 1 for an event occurring on the same day as a vaccination (and reported as starting after vaccination).

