**CONFIDENTIAL**

209538 (NTHI MCAT-009)  
 Statistical Analysis Plan Amendment 1

- Adverse event start dates with missing day and month:
  - If the event starts in the same year as at least one of the study doses, the contents of AE.AESTRTPT (the flag indicating if the event occurred before or after vaccination) will be used to complete the date. If ‘after vaccination’ is selected, the imputed start date will match the first (or only) study dose given during that year. If ‘before vaccination’ is selected, the imputed date will be one day before the first (or only) study dose given during that year.

All other cases of incomplete AE or concomitant medication/vaccination start date will follow the standard rules above.

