**10.1.3.6. Duration of events**

The duration of an event with a start and end date will be the number of days between the start and end dates plus 1 day, i.e. an event that starts on 03MAR2018 and ends on 12MAR2018 has a duration of 10 days.

The duration of solicited events will be calculated as the sum of the consecutive days with the symptom reported at Grade 1 or higher. The duration of solicited events at a specific grade (e.g. Grade 3) will be calculated as the sum of the consecutive days with the symptom reported at that grade. The same rule applies for solicited events ongoing at the end of the solicited follow-up period considering the maximum intensity reported.

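### SAP 10.1.2.1 sets a missing AE start day to the 15th in a month with no study dose, even when the recorded end date or the 30-day window shows an earlier start

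*SAP*

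**What the plan says.** The rule is in SAP Amendment 2, section 10.1.2.1 (Dates). The first SAP version and Amendment 1 carry the same text.

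- Default for partial dates used in calculations: "A missing day will be replaced by 15".
- Exception for AE start dates with a missing day: "If the event starts in the same month as at least one of the study doses". The before/after-vaccination flag then decides. An event flagged as after vaccination takes the date of the first study dose in that month; one flagged as before takes the day before it.
- Fallback: "All other cases of incomplete AE or concomitant medication/vaccination start date will follow the standard rules above".

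These dates feed the following:

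- The collection window for unsolicited AEs (SAP section 2, safety monitoring): "i.e. the day of vaccination and the 29 subsequent days". Protocol 12.5.8.1 requires recording of "All AEs during 30 days following administration of each dose of NTHi-Mcat study vaccine".
- The tables (SAP 5.4.1): the percentage of subjects with an unsolicited AE "reported up to 30 days after NTHi-Mcat vaccinations will be tabulated by group with exact 95% CI", repeated for Grade 3 and vaccine-related events.
- Onset day (SAP 10.1.3.5), counted from the last vaccination: "This is 1 for an event occurring on the same day as a vaccination".
- Duration (SAP 10.1.3.6): "will be the number of days between the start and end dates plus 1 day".

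**The concern.** A 30-day window usually runs into the next calendar month. That month normally holds no study dose, because the two NTHi-Mcat doses are 60 to 75 days apart (protocol Table 5), so the flag-based exception does not apply and the start becomes the 15th. If the window closes before the 15th, any event dated only to that month lands outside it. This happens even when the recorded end date proves that the event began inside.

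The 30-day unsolicited AE percentages and their Grade 3 and related subsets are at stake, as are the combined solicited and unsolicited tables. The rule can also produce a start date after the end date.

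**Working it through.** **The plan's own figure.** SAP 10.1.3.6 gives 3 to 12 March 2018 as 10 days: 12 - 3 + 1 = 10. It reproduces.

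**Worked case** (dates chosen for illustration). Dose on 10 March 2020; window to 8 April (10 March + 29 days). AE start 'April 2020', end 5 April 2020.

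- Possible true starts are 1 to 5 April. Onset day = start - dose + 1, so day 23 to day 27, all inside the window.
- Imputed start is 15 April: 36 days after the dose, onset day 37, outside the window.
- Duration = 5 - 15 + 1 = -9 days.

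Partial end dates have a similar fault. Start 20 March with end 'March' gives an end of 15 March and a duration of 15 - 20 + 1 = -4 days.

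**Which dose dates are exposed.** Let the dose fall on day D of a month with m days. The window reaches day n = D + 29 - m of the next month. Events there are moved out when 1 ≤ n ≤ 14, that is, when D lies between m - 28 and m - 15:

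| Days in month | Exposed dose days |
|---|---|
| 31 | 3 to 16 |
| 30 | 2 to 15 |
| 29 | 1 to 14 |

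This is 14 dates in each month. The window days moved out per month are 1 + 2 + ... + 14 = 105.

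**Share of window days, given a missing day.** The count covers all dose dates from the study start, 23 April 2019, to 31 December 2020 (end date assumed): 619 dates, or 619 × 30 = 18,570 window days, of which 8,904 fall in the next month.

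- Exposed dose dates: 20 full months × 14 = 280; 280/619 = 45%.
- Window days moved out: 20 × 105 = 2,100.
- Of next-month window days: 2,100/8,904 = 23.6%.
- Of all window days: 2,100/18,570 = 11.3%.

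If the table window is read as 31 days, the shares are 2,100/9,511 = 22.1% and 2,100/19,189 = 10.9%.

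These shares treat onset as uniform over the window. Weighting window day k (k = 0 to 29) by exp(-k/10) - exp(-(k+1)/10), an exponential onset with mean 10 days truncated at day 30 (assumed), gives about 12% of next-month onsets and 3% of all onsets.

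**The opposite error.** With a dose on 20 March the window ends on 18 April. An event that truly began on 25 April but is dated only 'April' is imputed to 15 April and counted. Over the same dose dates, with true onset on days 31 to 45 (619 × 15 = 9,285 pairs), 2,597 are pulled in: 28%.

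**The case against.** The strongest reply is that this is a narrow gap in a sponsor-wide standard rule, that it touches descriptive tables only, and that it may affect no events at all. Diary cards cover the dose day and the next 29 days and are verified with the subject (protocol 12.5.8), and monitors verify source data (protocol 12.4.8). The SAP does not say outright that window membership uses the imputed date. No described table of unsolicited AEs reports duration, so a negative duration may never be displayed.

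Most of this stands, and it limits the size. It does not remove the fault. Partial dates are used in calculations and onset day is derived from the start date, so the imputed date is the natural one to decide window membership. Nothing in SAP section 9 overrides the rule.

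A reader might infer that the percentages can only fall. The documents do not support that. Post-dose visits may take place 30 to 45 days after the dose (protocol Table 5), and some later events can be recorded and pulled in, as shown above. The error is mainly downward because non-serious AEs must be recorded only for the 30 days.

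A reader might also expect more partial dates in Sh_NTHi-Mcat_3 and Sh_NTHi-Mcat_6, where visits could be remote. Protocol 8.1 permits mailed diaries and remote safety follow-up, but nothing says that dates become less complete. No between-group bias is shown.

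**Conclusion.** The concern holds as a minor defect: a stated rule can override recorded information and misplace an event relative to the 30-day window. The exposure, given a missing day, is about 24% of next-month window days and 11% of all window days under uniform onset, or about 12% and 3% under the assumed early onset. These figures describe calendar exposure and should not be read as the proportion of AEs lost. The documents give no frequency of partial dates, so the number of events affected cannot be estimated and may be nil.

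SAE and potential immune-mediated disease summaries mostly use long periods (SAP 5.4.2.4), so the effect there is confined to events near a period boundary, such as the related-SAE period ending one month after Dose 2. The primary immunogenicity analysis does not use AE dates.

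**What to change.** Amend SAP 10.1.2.1 and leave the same-month exception with its before/after-vaccination flag unchanged. Add:

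1. When the day is missing and the AE month holds no study dose but begins within the 30-day window after an NTHi-Mcat dose, impute the start to the first day of that month.
2. In all other cases, an imputed start may not be later than the known end date.
3. An imputed end date may not be earlier than the start date.

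In the worked case this gives a start of 1 April, onset day 23 and a duration of 5 - 1 + 1 = 5 days.

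The cost is a few lines of SAP text and a small programming change. The downside is that some events that truly began after day 30 may be counted. In the same count for true onset on days 31 to 45, the share placed inside the window rises from 28% to 6,797/9,285 = 73%. Few such non-serious events should be on record, so the unsolicited AE count may be slightly higher.

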**CONFIDENTIAL**

209538 (NTHI MCAT-009)  
 Statistical Analysis Plan Amendment 1

- Adverse event start dates with missing day and month:
  - If the event starts in the same year as at least one of the study doses, the contents of AE.AESTRTPT (the flag indicating if the event occurred before or after vaccination) will be used to complete the date. If ‘after vaccination’ is selected, the imputed start date will match the first (or only) study dose given during that year. If ‘before vaccination’ is selected, the imputed date will be one day before the first (or only) study dose given during that year.

All other cases of incomplete AE or concomitant medication/vaccination start date will follow the standard rules above.

#### **10.1.2.2. Laboratory data**

Missing laboratory results (including immunological data) will not be replaced.

#### **10.1.2.3. Daily recording of solicited symptoms**

##### ***10.1.2.3.1. Studies with paper diaries***

Denominators for the summary of local (or general) solicited symptoms will be calculated using the number of subjects who respond “Yes” or “No” to the question concerning the occurrence of local (or general) symptoms.

When a specific symptom is marked as having not occurred following a specific vaccination (i.e. SDTM CE.CEOCCUR=N for the specified post-vaccination period for the symptom in question), all daily measurements will be imputed as Grade 0.

When a specific symptom is marked as having occurred following a specific vaccination (i.e. SDTM CE.CEOCCUR=Y for the specified post-vaccination period for the symptom in question), any missing daily recordings will be given imputed values to allow them to contribute to the ‘Any’ rows but not to specific grade rows of the symptom summary tables.

When the occurrence of a specific symptom is not present (i.e. SDTM CE.CEOCCUR is neither Y nor N for the specified post-vaccination period for the symptom in question) but the group of symptoms (local or general) is marked as having occurred (i.e. SDTM CE.CEOCCUR=Y), all missing daily recordings will be given imputed values to allow them to contribute to the ‘Any’ rows but not to specific grade rows of the symptom summary tables.

**CONFIDENTIAL**

209538 (NTHI MCAT-009)  
 Statistical Analysis Plan Amendment 1

The following table shows how subjects contribute to each category for a specific solicited symptom over the Day X to Day Y post-vaccination period:

Solicited symptom category	Subjects included in the calculation of the numerator
Any	All subjects with at least one occurrence of the symptom at Grade 1, Grade 2, or Grade 3 between Day X and Day Y or with the symptom marked as present and at least one missing daily recording between Day X and Day Y
At least Grade 1	All subjects with at least one occurrence of the symptom at Grade 1, Grade 2, or Grade 3 between Day X and Day Y
At least Grade 2	All subjects with at least one occurrence of the symptom at Grade 2 or Grade 3 between Day X and Day Y
At least Grade 3	All subjects with at least one occurrence of the symptom at Grade 3 between Day X and Day Y

#### **10.1.2.4. Unsolicited adverse events**

Missing severity, relationship with study vaccine, and outcome of unsolicited adverse events will not be replaced and will appear as 'UNKNOWN' in all statistical output.

#### **10.1.3. Data derivation**

##### **10.1.3.1. Age at vaccination in years**

When age at vaccination is to be displayed in years, it will be calculated as the number of complete calendar years between the date of birth and the date of vaccination. For example:

DOB = 10SEP1983, Date of vaccination = 09SEP2018 -> Age = 34 years

DOB = 10SEP1983, Date of vaccination = 10SEP2018 -> Age = 35 years

##### **10.1.3.2. Body mass index (BMI)**

BMI will be calculated as follows:

$$\text{BMI} = (\text{weight in kilograms}) / (\text{height in meters})^2$$

**CONFIDENTIAL**209538 (NTHI MCAT-009)  
Statistical Analysis Plan Amendment 1**10.1.3.3. Numerical serology results**

Numerical serology results will be derived from the content of IS.ISORRES in the SDTM dataset. For assays with a specific cut-off, the following derivation rules apply:

IS.ISORRES	Derived value
“NEG”, “-“, or “(-)”	cut-off/2
“POS”, “+”, or “(+)”	cut-off
“< value” and value is <= assay cut-off	cut-off/2
“< value” and value is > assay cut-off	value
“> value” and value is < assay cut-off	cut-off/2
“> value” and value is >= assay cut-off	value
“value” and value is < cut-off	cut-off/2
“value” and value is >= cut-off	value
All other cases	missing

**10.1.3.4. Geometric mean concentrations (GMCs)**

GMC calculations are performed by taking the inverse logarithm of the mean of the log-10 concentration transformations. Antibody concentrations below the cut-off of the assay will be given an arbitrary value of half the cut-off of the assay for the purpose of GMC calculation. The cut-off value is defined by the laboratory before the analysis and is described in the protocol.

**10.1.3.5. Onset day**

The onset day for an event (e.g. AE, medication, vaccination) is the number of days between the last study vaccination and the start date of the event. This is 1 for an event occurring on the same day as a vaccination (and reported as starting after vaccination).

**10.1.3.6. Duration of events**

The duration of an event with a start and end date will be the number of days between the start and end dates plus 1 day, i.e. an event that starts on 03MAR2018 and ends on 12MAR2018 has a duration of 10 days.

The duration of solicited events will be calculated as the sum of the consecutive days with the symptom reported at Grade 1 or higher. The duration of solicited events at a specific grade (e.g. Grade 3) will be calculated as the sum of the consecutive days with the symptom reported at that grade. The same rule applies for solicited events ongoing at the end of the solicited follow-up period considering the maximum intensity reported.

